6. POTENTIAL RISKS AND BENEFITS

6.1 POTENTIAL RISKS

Risks Associated With LTLR-WB: The whole blood product to be utilized starting in the prehospital environment in the pilot clinical trial is the identical product to be used in the hospital and identical to the current whole blood product that has been transfused in over 200 patients over the last 24 months at the University of Pittsburgh without evidence of complications or transfusion reactions. The primary risk with LTLR-WB is a hemolytic transfusion reaction which will be followed as an important secondary outcome. There have been no hemolytic transfusion reactions in over 200 patients transfused LTLR-WB at the University of Pittsburgh in the last 24 months. The primary risks with any blood transfusion can be found in the Circular of Information prepared jointly by AABB, the American Red Cross, America's Blood Centers, and the Armed Services Blood Program. Those primary acute immunologic complications include hemolytic transfusion reactions, immune mediated platelet destruction, febrile nonhemolytic reactions, allergic reactions, anaphylactoid reactions and transfusion-related acute lung injury (TRALI). Delayed immunologic complications include delayed hemolytic reaction, alloimmunization, posttransfusion purpura, transfusion-associated graft-vs-host disease. Nonimmunologic complications include transmission of infectious agents, bacterial sepsis, transfusion-associated circulatory overload (TACO), hypothermia and metabolic complications.

The primary risk associated with transfusion of Rh+ blood into a woman of child-bearing potential (WCP) is hemolytic disease of the fetus and newborn (HDFN) of a future pregnancy. Complications of HDFN include fetal anemia, fetal hydrops, and in the most severe cases, fetal death. However, the overall risk of poor fetal outcome in a future pregnancy for Rh- women that are administered Rh+ blood products has been estimated to be less than 0.5%⁹⁰. Of note, the incidence of a female being Rh- is only 15%. This means that the majority of WCP are at no risk of Rh mismatch. For those WCP that are at risk, the likelihood of poor fetal outcome is very small.

6.1.2 Risk of Study Procedures

Risk of breach of confidentiality: When the results of the research are published or discussed in conferences, no information will be included that would reveal subjects' identities. The PI and other study personnel will ensure that the subject's confidentiality will be maintained. Subject name and other identifiable information will be kept in a secure, locked, limited access area such as a password protected database. Subjects will be provided a unique study identification number.

Risk of venipuncture: Any labs drawn for research will try to be coordinated with labs being drawn for conventional care. Any venipuncture performed will be done so using aseptic technique by a clinical team member trained in phlebotomy.

6.2 ALTERNATIVE TREATMENTS

Prehospital air medical standard of care resuscitation and in-hospital standard of care resuscitation will be employed.

6.3 POTENTIAL BENEFITS

We anticipate that the benefits of getting whole blood may reduce bleeding in some patients, and possibly reduce overall blood transfusion requirements during the first day after injury. Prior studies have suggested that early whole blood transfusion may improve outcomes in patients with a lot of blood loss. Whether the subject receives the early whole blood transfusion, s/he may also benefit from increased observation at the time points involved in the study. Ultimately subject participation may help us to improve prehospital treatment of trauma injuries.

6.4 DATA SAFETY MONITORING

6.4.1 Data Safety Monitoring Board

The Clinical Coordinating Center will be led by [name] (PI) for the pilot trial with the assistance of MACRO and associated clinical research infrastructure at the University of Pittsburgh. Given the small size and resources allotted for the pilot trial, we will not have a formal Data Coordinating Center and the data coordination will be performed by the Clinical Coordinating Center. A Steering Committee chaired by [name] (Co-PI) will be charged with overseeing the study and make all major organizational and policy decisions. Committee members will include [name], [name] and [name]. This group will have conference calls as needed for smooth execution of the trial. Members of a Data Safety Monitoring Board (DSMB) will be appointed and will include experts in *hematology, surgery (trauma/critical medicine), bioethics, and biostatistics*. Members will consist of persons independent of the investigators who have no financial, scientific, or other conflict of interest with the study. Written documentation attesting to absence of conflict of interest will be required.

Any perceived or real conflicts of interest will be submitted to the University of Pittsburgh Conflict of Interest office. If required, a management plan will be instituted to manage the conflict of interest. At this time, no one on the study team has a conflict of interest.

6.4.2 Data Safety Monitoring Plan

The proposed study will use the FDA definition of adverse events (AE) and serious adverse events (SAE). Any fatal or life threatening AE, which is unexpected and related or possibly related to study intervention, will be reported immediately to the IRB and may be followed by an additional letter detailing the nature of the SAE if needed. In the event that a participant either withdraws from the study or the investigators decide to discontinue a participant due to a SAE, the participant will be monitored by the co-PIs until (a) a resolution is reached (e.g., the problem has resolved or stabilized with no further change expected), (b) the SAE is determined to be clearly unrelated to the study intervention, or (c) the SAE results in death. Outcomes of related or possibly related SAEs will be regularly reported to the IRB, DSMB, and the sponsor. A summary of the SAEs that occurred during the previous year will be included in the annual progress report as well as in the annual IRB renewal.

Our DSMB responsibilities are listed as an appendix (Appendix 2). The DSMB will monitor accruing data in order to confirm patient safety throughout the trial. All study personnel will be trained on the protection of human subjects. Although the DSMB will make the final decision about the monitoring plan, we anticipate that the DSMB will evaluate the rate of adverse events between the treatment and control arms every 6 months during enrollment. The DSMB will also monitor primary, secondary study outcomes between the treatment and control groups including

main effects and a priori subgroups as specified elsewhere in the protocol. The DSMB will advise the investigators if a change in the protocol is warranted based on this monitoring.

The Medical Monitor is required to review all unexpected serious adverse events and other unanticipated problems involving risk to subjects or others. At a minimum, the medical monitor must comment on the outcomes of the event or problem and, in case of a serious adverse event, comment on the relationship to participation in the study. The Medical Monitor may review unblinded data in order to assist with his review.

Study Changes

If the PI and study team plan to modify the study, they will submit the amendment to the University of Pittsburgh HRPO along with all study documents to be changed (i.e. protocol, consent form, etc.) Once IRB approval is obtained, the study team will submit the changes to the NIH at the next reporting cycle unless earlier notification is warranted. If it is a significant change, the PI will request approval by the NIH Program Officer and DSMB prior to modification. Any changes will also be reviewed by the Office for Investigator-Sponsored IND and IDE Support (O3IS) for determination if the change requires prospective FDA review or if it can be submitted at annual report.

Data Analysis Plan Overall guideline:

- 1. Nature of this study: Pilot study
- 2. Overall objectives: Evaluate safety, efficacy, and feasibility of a LTLR-WB prehospital thru in-hospital protocol. The study will provide estimation for intra-cluster correlation coefficient and sample size variation across clusters for the design for a future full scope large clinical trail
- 3. Analysis Principle: Intent-to-treat for the prehospital randomization assignment. 95% confidence intervals for all measurements

Safety and Efficacy Analysis:

- 1. In-hospital mortality is the primary safety and efficacy outcome and will be compared across randomized groups.
- 2. LTLR-WB and Standard of Care arms will be compared using a pooled Z test of two independent proportions.
- 3. Survival analysis will be conducting looking at median survival at 3hr, 6hr, 24hr, and 28day time points across the two arms of the study testing the differences using log rank test.

Eligibility, Enrollment, and Subject Accrual:

The feasibility of enrollment will be evaluated by determining, ratio of the following parameters will be calculated along with 95% confidence intervals:

- 1) the number of patients that meet the eligibility criteria for the trial;
- 2) the proportion of eligible patients that can be randomized and

3) the proportion of eligible patients who are enrolled in the trial.

Additionally:

1. The reasons of not enrollment will be recorded with related frequency and percentages.

- 2. Frequency of patients eligible but not enrolled will be recorded
- 3. Frequency of patients randomized but not included in the study will be recorded
- 4. Rate of subjects' accrual per month with 95% C.I. will be calculated.
- 5. Adherence rates for each treatment arm of the protocol will be ascertained and recorded as the proportion of enrolled patient who adhere to each of the study arms

Interim Analysis

The main points in the interim analysis:

- 1. Monitor the eligibility, enrollment, and subject accrual as stated above.
- 2. Safety and efficacy by looking for In-hospital mortality differences between LTLR-WB and Standard of Care arms and compared these ratios using a pooled Z test of two independent proportions. Stopping rules will be used in the study interim analysis.
- 3. Survival analysis will be monitored in the interim analysis
- 4. Secondary outcomes will be checked and related 95% C.I will be estimated across the study two arms.
- 5. Unanticipated Events
- 6. Protocol deviation

Stopping rules

The following stopping rules of O'brien-Fleming boundaries will be implemented in the interim analysis:

Details wher	Spending	= O'Brien-	Fleming, N1	l = 56, N2 =	56, P1 = 0.1	100, $P2 = 0$.3300
Look Time	Lower Bndry	Upper Bndry	Nominal Alpha	Inc Alpha	Total Alpha	Inc Power	Total Power
2 1.00	-1.96857	1.96857	0.049002	0.046949	0.050000	0.636252	0.800921
Drift2.81024	4 3.5 3 2.5 1.5 1.5 1.5 1.5 0 7 2 5 0 7 7 7 7 5 7 7 7 7 7 7 7 7 7 7 7 7 7	O'Brien-F	leming Bound	daries with Al	pha = 0.05	×.	

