Version # and Date:	Version 7 Dated 2020-02-04						
Clinical Phase:	Phase 3						
Investigational Drugs:	Low titer, platelet replete-leukocyte reduced, group O whole blood						
Trial Site:	University of Pittsburgh						
IND Sponsor:	[name], MPH						
Investigator:	[name], MPH						
Co-Principal	[name]						
Investigator							
Sub-Investigators:	[name] [name]; [name]; [name], PhD; [name]						
Research Facilities:	UPMC Presbyterian/ Montefiore						
Clinical Laboratories:	UPMC Presbyterian Shadyside CP PUH- UPMC Clinical Laboratory Building						
Study Rationale:	Initiation of whole blood resuscitation in the prehospital setting and continued through the in-hospital phase of treatment to patients in hemorrhagic shock represents the most efficacious and ideal intervention post-injury.]					
Study Objectives:	The objective of this study is to determine whether LTLR-WB resuscitation in the prehospital setting with continuation through the in-hospital acute resuscitation phase of care will significantly reduce the morbidity and mortality attributable to hemorrhagic shock post-injury as compared to standard prehospital and in-hospital resuscitation practice.						
Study Hypothesis:	Early whole blood transfusion initiated in the prehospital settin and continued through the in-hospital acute resuscitation phase of treatment will reduce the morbidity and mortality attributable to hemorrhagic shock post-injury as compared to standard prehospital and in-hospital resuscitation practice	ıg					
Study Aims:	Specific Aim I: Determine the feasibility and most appropriate study population that will lead to a large multicenter clinical tria designed to evaluate the effectiveness of prehospital through in-hospital LTLR-WB as compared to standard care practice in patients at risk of hemorrhagic shock. Specific Aim II: Determine if prehospital through in-hospital LTLR-WB reduces 28-day mortality, multiple organ dysfunction, presenting coagulopathy, 24-hour resuscitation requirements and early mortality time points as compared to	al n					

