1.2 SPECIFIC AIMS

Hypothesis: The initiation of LTLR-WB resuscitation in the prehospital setting with continuation through the in-hospital acute resuscitation phase of care will significantly reduce the morbidity and mortality attributable to hemorrhagic shock post-injury as compared to standard prehospital and in-hospital resuscitation practice.

Specific Aims:

Specific Aim I: Determine the feasibility and most appropriate study population that will lead to a large multicenter clinical trial designed to evaluate the effectiveness of prehospital through inhospital LTLR-WB as compared to standard care practice in patients at risk of hemorrhagic shock.

Specific Aim II: Determine if prehospital through in-hospital LTLR-WB reduces 28-day mortality, in-hospital mortality, multiple organ dysfunction, presenting coagulopathy, 24-hour resuscitation requirements and early mortality as compared to standard of care prehospital and in-hospital resuscitation in patients at risk of hemorrhagic shock.

Specific Aim III: Determine the primary drivers by which prehospital through in-hospital LTLR-WB improves clinical, resuscitative and hemostatic outcomes as compared to standard of care prehospital and in-hospital resuscitation in patients at risk of hemorrhagic shock.

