2.8 STUDY ENDPOINTS

Principle Outcomes: The principle objectives for the pilot trial are to evaluate 1.) safety and efficacy and 2.) feasibility for a prehospital through in-hospital LTLR-WB resuscitation protocol that will lead to a large, multicenter clinical trial that can be performed under the requirements of *exception from informed consent for emergency research* with regulatory oversight by the Food and Drug Administration (FDA) and Title 21, Code of Federal Regulations, Section 50.24 (21 CFR 50.24).

Primary Outcome For Assessing Safety and Efficacy: The primary safety and efficacy outcome for the pilot trial will be all cause 28-day mortality. We will utilize data derived from our recently completed PAMPer trial, which utilized identical inclusion and exclusion criteria, for inhospital mortality estimates.

Primary Outcome For Assessing Feasibility and Trial Performance: The primary feasibility outcome for the pilot trial will be enrollment and accrual rate. Secondary performance and feasibility outcomes will include a) Eligibility rates; b) Adherence rates for the protocol; c) Injury and patient characteristics enrolled in the trial; d) Frequencies of proposed clinical outcomes; e) Air medical base population differences.

Secondary Clinical Outcomes Estimating Treatment Effectiveness and Safety: Over 28 days or up to discharge following randomization, we will compare: 1) Multiple Organ Failure (MOF): Organ dysfunction will be evaluated via the Denver Post-Injury Multiple Organ Failure Score and characterized as both a rate (%) and as MOF free days.^{84,85} 2) Mean Denver Post-injury MOF Score: This continuous variable will be a much more sensitive measure of organ dysfunction for the pilot trial. 3) Arrival Shock Severity: We will compare presenting base deficit,

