lactate and shock index (SI, heart rate/systolic blood pressure-bpm/mmHg) 4) Acute Respiratory Distress Syndrome (ARDS): We will compare pulmonary dysfunction using the Berlin definition for ARDS.⁸⁶ 5) Nosocomial Infection (NI): We will compare the incidence of pneumonia and blood stream infections. 6) Mortality: We will compare mortality rates at 3, 6 and 24 hours following arrival, all cause in-hospital and 28-day mortality. 7) Blood component transfusion and resuscitation requirements at 24 hours: We will compare overall blood component transfusion requirements and crystalloid/colloid resuscitation requirements across the two arms. 8) Acute Hemolytic Transfusion Reaction (AHTR): We will compare the incidence of AHTRs across study arms as defined by the CDC/National Healthcare Safety Network (NHSN) Hemovigilance Surveillance definition. (www.cdc.gov/nhsn) Length of hospital stay and intensive care unit stay. Length of stay and ICU resources will be descriptively compared. Patients will be followed for 28 days from admission for the 28-day mortality outcome utilizing chart review, patient contact or utilization of the social security death index for those who cannot be contacted.

Predefined Subgroup Analyses: Predefined subset analyses for the pilot trial will be performed looking at our primary outcomes (safety/efficacy and feasibility) in 1) Females > 50 years of age versus study cohort with females < 50 years excluded ; 2) Patients who ultimately did or did not require in-hospital blood transfusion; 3) Patients with and without significant traumatic brain injury (Head abbreviated injury score- AIS >2); 4) Patients enrolled from the scene of injury versus those enrolled from a referral hospital; 5) Patients that require operative intervention in the first 24 hours; 6) Those patients with a preinjury history of anticoagulation / antiplatelet therapy; 7) Patients who ultimately did or did not require massive transfusion (≥ 10 units blood in first 24 hrs) 8)Patients who did or did not receive prehospital PRBCs.

Clinical Outcome Definitions:

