2.9 STATISTICAL ANALYSIS

The overarching goals for the pilot trial are to evaluate safety, efficacy and feasibility of a LTLR-WB prehospital through in-hospital protocol to plan for the successful execution of a large, multicenter clinical trial. All analyses will be performed based on the intent-to-treat principle for the prehospital randomization and analyses will include all enrolled patients grouped by randomization assignment. This pilot study will guide the calculation needed for the large, multicenter clinical trial and will provide estimation for intra-cluster correlation coefficient and sample size variation across clusters. We will report 95% confidence intervals for all measurements

Safety and Efficacy Analysis: 28-day mortality is the primary safety and efficacy outcome and will be compared across randomized groups. Utilizing intention to treat principles we will compare the LTLR-WB and Standard of Care arms using a pooled Z test for comparing two independent proportions. We will additionally perform survival analysis for all mortality outcomes including 3hr, 6hr, 24hr, and 28day time points across the two arms of the study testing the differences using log rank test.

Eligibility, Enrollment, and Subject Accrual Anlaysis: The feasibility of enrollment will be evaluated by determining 1) the number of patients that meet the eligibility criteria for the trial; 2) the proportion of eligible patients that can be randomized and 3) the proportion of eligible patients who are enrolled in the trial. These proportions will be estimated directly as the observed ratio of numbers of patients, and 95% confidence intervals will be calculated to understand the likely range of values for a larger study with a comparable research protocol. The reasons why patients are not enrolled including frequencies of individual exclusions and the proportion of patients declining participation or not able to be randomized will be described. Rate of subjects' accrual per month with 95% C.I. will be calculated.

Adherence and Minimization of Bias: Adherence rates for each treatment arm of the protocol will be ascertained as the proportion of enrolled patients who adhere to the intervention (LTLR-WB vs. standard care) as assigned. Estimated proportions and 95% confidence intervals will be created. The trial has been designed to negate intervention arm crossover and maximize follow-up completion.

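### Two different mortality outcomes are each named primary, and the power and stopping rule belong to only one of them

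*Combined protocol and SAP*

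**What the plan says.** Two groups of current text disagree.

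**28-day mortality is primary.** Section 2.8: "The primary safety and efficacy outcome for the pilot trial will be all cause 28-day mortality". Section 2.9, Safety and Efficacy Analysis: "28-day mortality is the primary safety and efficacy outcome and will be compared across randomized groups".

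**In-hospital mortality is primary.** Section 6.4.2, Data Analysis Plan, repeats the Section 2.9 sentence with the other outcome: "In-hospital mortality is the primary safety and efficacy outcome and will be compared across randomized groups". The same outcome is used in:
- the sample size text in Section 2.9 and its repeat in Section 6.4.7 (33% versus 11%);
- item 2 of the interim analysis in Section 6.4.2, to which the O'Brien-Fleming stopping rules are attached;
- the Z-test row of Appendix 8, Table 2.

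Other places do not settle it:
- Section 2.8 also lists both among the secondary outcomes: "We will compare mortality rates at 3, 6 and 24 hours following arrival, all cause in-hospital and 28-day mortality". The secondary-outcome text in Section 2.9 and Appendix 8 Table 4 list 28-day mortality again.
- Specific Aim II omits in-hospital mortality in the Synopsis ("reduces 28-day mortality, multiple organ dysfunction, presenting coagulopathy") but includes it in Section 1.2 ("reduces 28-day mortality, in-hospital mortality, multiple organ dysfunction").
- On planning rates, Section 2.8 says: "We will utilize data derived from our recently completed PAMPer trial, which utilized identical inclusion and exclusion criteria, for inhospital mortality estimates".

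Separately, the outcome definitions in Section 2.8 call the mean Denver score the pilot's primary endpoint, although the same section lists it as secondary.

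**The concern.** The two outcomes differ in the plan's own terms. Section 2.8 plans follow-up to 28 days from admission, including contact with patients and a death-index search, so deaths after discharge are meant to count for 28-day mortality. They cannot count for in-hospital mortality. An in-hospital death after day 28 does the reverse. The window for secondary outcomes ("Over 28 days or up to discharge following randomization, we will compare") leaves it unclear whether such a death would be captured.

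Three things are at stake.

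1. The stopping boundary is applied to an outcome that Sections 2.8 and 2.9 do not call primary. If the final test follows Section 2.9, the two looks test different outcomes, and the boundary table no longer describes one sequence of tests.
2. The trial is open label. While the primary outcome is unsettled, it could be chosen after results by arm are known.
3. The only power figure belongs to in-hospital mortality.

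**Working it through.** **Inputs.** Section 2.9, Sample Size Justification: control 33%, LTLR-WB 11%, 56 per arm, two-sided alpha 0.05, looks at information times 0.50 and 1.00, boundaries ±2.96259 and ±1.96857. Section 2.9, Safety and Efficacy Analysis: pooled Z test. Clustering is ignored here, as it is in the plan's own calculation.

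**Step 1. Reproduce the plan's figure.** Drift = (p_C − p_T) / √[2·p̄(1 − p̄)/n], with p̄ the mean of the two rates. Here p̄ = (0.33 + 0.11)/2 = 0.22, so drift = 0.22 / √(2 × 0.22 × 0.78 / 56) = 2.8102 (stated 2.81024). Power is the bivariate normal probability of crossing either boundary, with correlation √0.5 between looks.

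| Quantity | Recomputed | Stated |
|---|---|---|
| First-look alpha | 0.003051 | 0.003051 |
| Total alpha | 0.0500 | 0.050000 |
| First-look power | 0.1647 | 0.164669 |
| Total power | 0.8010 | 0.800921 |

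The arithmetic is right for in-hospital mortality.

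**Step 2. Try to carry it to 28-day mortality.** The documents give no 28-day control rate. They give 33% in-hospital (Section 2.9), 30% overall mortality with no time horizon (Section 2.2), and 30–40% before discharge (Appendix 4). I therefore assume 28-day control rates of 30% to 40% and add 25% as a lower margin that no section supports. Two readings of the planned effect are possible: relative risk 0.11/0.33 = 1/3, or a 22-point difference.

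| Assumed control rate | LTLR-WB at RR 1/3 | Drift | Power | LTLR-WB at 22 points | Drift | Power |
|---|---|---|---|---|---|---|
| 25% | 8.3% | 2.366 | 66% | 3% | 3.355 | 92% |
| 30% | 10% | 2.646 | 75% | 8% | 2.967 | 84% |
| 33% | 11% | 2.810 | 80% | 11% | 2.810 | 80% |
| 40% | 13.3% | 3.191 | 89% | 18% | 2.566 | 73% |

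An exact two-stage binomial check (28, then 56 per arm) at 25/30/33/40% gives 68/78/83/91% at fixed relative risk and 96/87/83/74% at a fixed 22 points. The directions are the same. The normal approximation is rough where the LTLR-WB rate is 3%.

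**Step 3. How often could the choice change the final result?** No section gives the share of patients whom the two outcomes classify differently, so this is illustration only. It uses 400,000 simulated trials per cell, with both outcomes tested at the final boundary 1.96857.

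| Patients classified differently | 1% | 2% | 3% | 5% |
|---|---|---|---|---|
| Tests disagree, 33% vs 11%, even split of the two kinds of death | 4.8% | 7.4% | 9.2% | 12.1% |
| Same, only post-discharge deaths differ | 5.0% | 7.9% | 9.9% | 13.3% |
| Same, only late in-hospital deaths differ | 4.8% | 7.4% | 9.3% | 11.9% |
| Tests disagree, no effect (33% in both arms), even split | 1.8% | 2.7% | 3.4% | 4.4% |

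With no effect, the one-way cases give 1.7% to 4.3%. Nothing was computed at the interim boundary.

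**Step 4. False-positive error if the looks use different outcomes.** Adding the nominal levels bounds it: 0.003051 + 0.049002 = 0.052053. The harm is therefore an undefined claim and stopping decision, with little inflation of error.

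**The case against.** The strongest reply is that Section 2.8 names 28-day mortality and then says that the earlier trial supplies in-hospital estimates. That reads as a deliberate planning proxy, so the power gap is an unstated assumption and not a second contradiction. The sample-size wording about the primary outcome may also describe the earlier trial. Both outcomes will be reported with 95% intervals, in a pilot that has a separate primary feasibility outcome, so neither result would be hidden. Section 2.8 does define both outcomes from the date of admission. The 25% row lies below the documents' figures, and the disagreement rates rest on an assumed discordance.

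Much of this is fair. The power range to rely on is 30% to 40%, the simulation should carry little weight, and nothing here shows that the trial is underpowered. But a proxy rate explains only the 33% input. It does not explain why the Data Analysis Plan names in-hospital mortality as primary, or why the stopping test and the Table 2 Z test use it. Reporting both outcomes does not say which one the formal test and the boundary apply to. The pilot has a powered efficacy comparison with formal stopping rules, so that has to be stated. A common starting date also leaves in-hospital deaths after day 28 unresolved.

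**Conclusion.** The concern holds. The primary safety and efficacy outcome is contradictory in current text and must be settled before outcomes are compared by arm. The contradiction rests on the wording alone and needs no assumption.

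The 80% power is correct for in-hospital mortality of 33% versus 11% and carries over to 28-day mortality only if the rates are the same. Over assumed control rates of 30% to 40%, 28-day power is 75% to 89% at a fixed relative risk, or 84% to 73% at a fixed 22-point difference. The direction depends on which effect is held constant, so 28-day power is not established either way. The effect of the choice on the final test cannot be sized from the documents.

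**What to change.** Name one primary mortality outcome and list the other as secondary. Use it in Sections 2.8 and 2.9, Section 6.4.2 (analysis item 1 and interim item 2), the sample size text in Sections 2.9 and 6.4.7, and Appendix 8 Tables 2 and 4. Either choice is workable:

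- **28-day mortality.** Sections 2.8 and 2.9 already name it, its horizon is fixed, and its follow-up is planned. Use 28-day status at the interim look, state that 33% is an in-hospital proxy, and show power over a range of control rates under both a fixed relative risk and a fixed 22-point difference. Cost: a short power table, an interim look that waits for 28-day status, and an 80% figure that becomes conditional.
- **In-hospital mortality.** Amend Sections 2.8 and 2.9 and state whether in-hospital deaths after day 28 count. Cost: a horizon that varies by patient.

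In both cases, remove the primary-endpoint label from the Denver score definition in Section 2.8, and make clear that the main clinical outcome in the secondary-outcome text of Section 2.9 means the main secondary outcome. The change is a protocol and SAP text amendment and needs no new data.
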